**In case of questions about the study or the medication card, please call:**

- Name: \_\_\_\_\_
- Phone number: \_\_\_\_\_

REFERENCES.....	15

AMENDMENT HISTORY

Not applicable.

ABBREVIATIONS

AE	adverse event
BMI	body mass index
CI	confidence interval
eCRF	electronic case report form
LTFU	long-term follow-up
MedDRA	medical dictionary for regulatory activities
PRESORS	pediatric RSV electronic severity and outcomes rating scale
RSV	respiratory syncytial virus
SAE	serious adverse event
SAP	statistical analysis plan
WHO-DD	World Health Organization drug dictionary

1. INTRODUCTION

This statistical analysis plan (SAP) contains definitions of analysis sets, derived variables and statistical methods for the analysis of safety for the final analysis of Study 64041575RSV2002 and should be considered in conjunction with the clinical trial protocol.²

1.1. Trial Objectives

Primary Objectives

The primary objectives are to evaluate in infants and children who have been treated with lumicitabine or placebo in Study 64041575RSV2004¹ during the follow-up period and within 2 years after the RSV infection:

- The incidence of the clinical diagnosis of asthma.
- The frequency of wheezing.

Secondary Objectives

The secondary objectives are to evaluate during the follow-up period in infants and children who have been treated with lumicitabine or placebo in Study 64041575RSV2004:

- The frequency of wheezing over time.
- The frequency of wheezing episodes over time.
- The long-term safety of lumicitabine.
- The frequency and type of respiratory infections.
- Medical resource utilization.

Exploratory Objectives

The exploratory objectives are to evaluate during the follow-up period in infants and children who have been treated with lumicitabine or placebo in Study 64041575RSV2004:

- The long-term impact of RSV and its treatment with lumicitabine or placebo on how the subject's health affects normal daily activities for subjects, parents/caregivers, and other family members.
- Impact of the type of wheezing/asthma phenotypes on the frequency of wheezing and clinical diagnosis of asthma.

1.2. Trial Design

This is a global, multicenter, blinded, LTFU study to evaluate the incidence of the clinical diagnosis of asthma and the frequency of wheezing in infants and children (otherwise healthy or with underlying comorbidities for severe RSV) who have completed their treatment course and their last study-related visit in a previous Phase 2 study, 64041575RSV2004, in which they received lumicitabine or placebo for the treatment of RSV infection. Subjects will be followed for at least 2 years following treatment. This study may be extended up to an additional 3 years (i.e., total duration up to 5 years after randomization into Study 64041575RSV2004). Participation in this LTFU study is optional for study sites. This LTFU study will be offered to subjects of Study 64041575RSV2004 if their site decides to participate in this LTFU study.

Subjects will be enrolled within 3 months after randomization in Study 64041575RSV2004.

No study drug will be administered in this study. The parent/caregiver of the subject and the investigator will remain blinded to the study treatment (lumicitabine or placebo) administered in Study 64041575RSV2004 until the completion of this LTFU study, including any extension period.

Assessments will be performed at the study site at enrollment in this study and at 3, 6, 12, 18, and 24 months after randomization in Study 64041575RSV2004. The last visit of Study 64041575RSV2004 may be combined with the entry visit of this LTFU study. The same assessments will be performed during monthly phone calls with the parent/caregiver between the study site visits.

More details can be found in the Time-and-Event schedule in the study protocol.

1.3. Statistical Hypotheses for Trial Objectives

No formal hypothesis testing will be performed. The hypothesis to be explored is that treatment of RSV-infected infants and children with lumicitabine will decrease the incidence of subsequent asthma and/or wheezing compared with infants and children treated with placebo.

1.4. Sample Size Justification

No formal power calculation has been performed, as this is an LTFU study in which infants and children from the previous Phase 2 study of lumicitabine (Study 64041575RSV2004) may be enrolled.

The planned number of subjects enrolled in Study 64041575RSV2004 is up to 120 subjects on lumicitabine and up to 60 subjects on placebo. It was expected that approximately 35% of those subjects were to participate in this LTFU study.

1.5. Randomization and Blinding

Randomization is not applicable in this study since it is the LTFU of Study 64041575RSV2004.

The parent/caregiver of subjects who enroll in this study and their investigators were to remain blinded to the study treatment (lumicitabine or placebo) administered in the previous Study 64041575RSV2004 until the completion of this LTFU study, including any extension period.

2. GENERAL ANALYSIS DEFINITIONS

2.1. Visit Windows and Phase definition

As this is a LTFU of Study 64041575RSV2004, only 1 analysis phase will be defined (see [Table 1](#)). The reference is the date of informed consent in study 64041575RSV2002.

Table 1: Trial Phase

Trial Phase	Trial Phase (Numeric Version)	Start Date	End Date
Long Term Follow Up	1	00:00 of the date of signing the informed consent	Trial termination date (date of last contact) with timestamp 23:59

For assigning assessments, the visit schedule as reported in the database will be used.

If a subject has a missing visit, the data will be set to missing and will not be imputed. Information of an unscheduled visit will be merged with the scheduled visit, meaning that any information will be added to scheduled visit data.

2.2. Pooling Algorithm for Analysis Centers

No pooling algorithm for analysis centers will be specified.

2.3. Analysis Sets

2.3.1. All Enrolled Analysis Set

The All Enrolled analysis set includes all subjects who were enrolled in this LTFU study. The All Enrolled set will be analyzed as treated.

2.4. Definition of Subgroups and Subsets

As study 64041575RSV2002 only included 7 subjects, no subgroups or subsets will be defined.

2.5. Study Day and Relative Day

The reference day is the date of informed consent in study 64041575RSV2002. All assessments will be assigned a day relative to this day.

The relative day for a visit is defined as:

$$\text{Visit day} - (\text{informed consent in study 64041575RSV2002}) + 1$$

For the monthly reports, the visit schedule will be based on the entry dates of each monthly report; the entry of the first report is the Screening visit, and each subsequent entry is considered as the next Monthly report (starting with Month 2, reflecting the time since the RSV event).

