- f. Medication use will be monitored throughout the study from signing of the informed consent form until the last study-related activity. Parents/caregivers will be required to bring all medications to the study site visit. Additionally, parents/caregivers will be required to document on a daily basis use of all medications on a medication parent/caregiver card, which will serve as a reminder card to be used during the study site visits and during the monthly phone calls between the study site visits for recording the medication used for respiratory infections and illnesses in the eCRF by the study site personnel. Parents/caregivers will be required to return the completed parent/caregiver cards to the study sites every 3 months (eg, in person or by mail/email/fax when no study site visit is scheduled).
- g. Collection of data on wheezing, asthma, eczema, allergic rhinitis, and impact of the subject's health status on normal daily activities for subjects, parents/caregivers, and other family members using a standardized questionnaire. The questionnaire should preferably be completed by the same study site responsible person, by

interviewing the subject's parent/caregiver. Parents/caregivers will complete the wheezing and medication parent/caregiver cards on a daily basis, which will aid the study site responsible person in completing the questionnaire during the interview. Parents/caregivers will be required to return the completed parent/caregiver cards to the study sites every 3 months (eg, in person or by mail/email/fax when no study site visit is scheduled).

- h. Once per calendar month ( $\pm 7$  days) from the entry visit.
- i. Data from lung function tests and allergy tests (immunoglobulin E and skin test), if available, will be collected as supporting documentation of the diagnosis of asthma, wheezing, and atopy as reported by the parent/caregiver.
- j. Medical resource utilization will be monitored throughout the study from signing of the informed consent form until the last study-related activity and will include medical visits, emergency room visits, and hospitalizations, all for respiratory conditions only and will be recorded in the eCRF. Visits with each type of health care provider (eg, general practitioner, pediatrician, physician assistant, nurse practitioner, pulmonologist, allergist, or other) will be specified in the eCRF.

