#### 9.1.2. Entry Visit

Screening can be performed as soon as it is confirmed that the subject participated in Study 64041575RSV2004 and completed the planned course of the study drug and the last study-related visit. Subjects may be enrolled within 3 months after randomization in Study 64041575RSV2004. The last visit of Study 64041575RSV2004 (ie, Day 28) may be combined with the entry visit of this LTFU study (Study 64041575RSV2002).

At the entry visit, after signing the ICF, the overall eligibility of the subject to participate in the study will be assessed.

Baseline demographics and medical/family history from the previous Phase 2 Study 64041575RSV2004 will be captured in the LTFU (Study 64041575RSV2002) eCRF. Medical and family history to identify risk factors for wheezing/asthma at baseline, including prenatal smoking by the subject's mother, subject's exposure to tobacco smoke, wheezing associated with symptoms of acute respiratory infections, whether the subject has siblings or attends kindergarten/day care, and personal and/or family history of atopy/allergy will be recorded in the eCRF.

Parents/caregivers will be provided with the medication and wheezing parent/caregiver cards, both of which need to be completed on a daily basis (see [Attachment 3](#) and [Attachment 4](#)).

During the entry visit, a clinical questionnaire (see [Attachment 2](#)) needs to be completed by a study site responsible person, by interviewing the subject's parent/caregiver, to collect the following information:

- Wheezing.
- Diagnosis of asthma, eczema, and allergic rhinitis. All medical information needed to confirm the diagnosis of asthma, eczema, and allergic rhinitis needs to be collected by the study site personnel.
- Impact of the subject's health status on normal daily activities for subjects, parents/caregivers, and other family members.

This questionnaire will capture information since the last study visit:

- If the entry visit of Study 64041575RSV2002 coincides with the last visit of Study 64041575RSV2004 (ie, Day 28), the "last study visit" in the questionnaire refers to

the Day 14 visit in Study 64041575RSV2004. Any recalled events in the questionnaire will be related to this time period.

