- If the entry visit of Study 64041575RSV2002 takes place after the last visit of Study 64041575RSV2004 (ie, Day 28), the “last study visit” in the questionnaire refers to the Day 28 visit in Study 64041575RSV2004. Any recalled events in the questionnaire will be in the last 30 days or less (if the entry visit to last study visit of Study 64041575RSV2004 is less than 30 days).

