5.3. Exploratory Endpoints

5.3.1. Definition

For the exploratory endpoints the data will be presented using for each subject a row for each month (based on the assignment in the database), and columns presenting the data to each subsequent question of the interview.

The same lay-out will be used to provide summary statistics for endpoints as defined below by treatment group and study Month. The definitions of these endpoints are given in [Table 3](#). Parameters will be assigned to the monthly visits based on the assignment in the database.

Table 3: Calculations and Conversion Formulae (Exploratory Endpoints)

Measurement	Calculation
Subject's daily activities limited by the subject's health per Month	The parent/caregiver reports that they are not working due to the child's health problems. The answer to Questionnaire section E question 1. The result will be either "Yes" or "No" and will be calculated for Screening and each Month as based on the assignment in the database.
Percentage of days per Month the parent/caregiver missed from work due to the subject's health	This is only calculated for parents/caregivers that were working, OR not working due to the child's health problems. If the parent is not working due to the child's health problems this is set to 100%. In all other cases total number of days missed from work because of the child's health problems, divided by the end date - start date +1 of the reported Month x100% and rounded to the nearest integer. The answer to Questionnaire section E question 1.
Parent's/caregiver's productivity at work limited by the subject's health per Month	This is only calculated for parents/caregivers that were working. The extent to which the parent's/caregiver's productivity while at work was limited by the subject's health per Month. The answer to Questionnaire section E question 1b.
Subject's health problems limited the parent's/caregiver's ability to engage in normal daily activities per Month	The extent to which the subject's health problems limited the parent's/caregiver's ability to engage in normal daily activities per Month. The answer to Questionnaire section E question 2.
How much the child's health has affected the child's usual activities per Month	The extent to which the child's health affected the child's usual activities per Month. The answer to Questionnaire section E question 3.

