Impact of the subject's health problems on the parent's/caregiver's health per Month	The extent to which the subject's health problems impacted the parent's/caregiver's health per Month. The answer to Questionnaire section E question 4.
Inability of the parent/caregiver to care for other family members due to the subject's health per Month	The inability of the parent/caregiver to care for other family members due to the subject's health per Month. The answer to Questionnaire section E question 5. The result will be either "Yes" or "No".
Subject's health limited the parent's/caregiver's time spent with other family members each Month	The extent to which the subject's health limited the parent's/caregiver's time spent with other family members each Month.

	The answer to Questionnaire section E question 6. The result will be categorical as listed in the Questionnaire.
Percentage of days other family members missed from work due to the subject's health problems per Month	The percentage of days each Month that other family members missed from work due to the subject's health problems. Derived base on the Questionnaire section E question 7. Calculated as the number of days as recorded in question 7 divided by the number of days since the last study visit/telephone call. For subjects currently not in paid employment, the value will be 100% for parents/caregivers who were not employed due to the child's health problem and missing if this was not due the child's health problem.
Clinical diagnosis of eczema within the first 2 years after the RSV infection	Clinical diagnosis of eczema within the first 2 years after the RSV infection, as diagnosed by a physician and reported by the parent/caregiver. The result will be either "Yes" or "No". Derived based on the answer to Questionnaire section C until the Month 24 analysis visit.
Clinical diagnosis of allergic rhinitis within the first 2 years after the RSV infection	Clinical diagnosis of allergic rhinitis within the first 2 years after the RSV infection, as diagnosed by a physician and reported by the parent/caregiver. The result will be either "Yes" or "No". Derived based on the answer to Questionnaire section D until the Month 24 analysis visit.

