5.3.2. Analysis Methods

Descriptive statistics and frequency tabulations will be used to present the parameters of long-term impact of RSV and its treatment with lumicitabine or placebo by previous treatment group at each analysis visit. For parameters that have continuous results (where the result is based on a scale from 0 to 10) descriptive statistics will be used, for the parameters with categorical results frequency tabulation will be used. The results will be presented graphically over time (mean for continuous parameters, stacked bar charts for categorical parameters).

Clinical diagnosis of eczema and allergic rhinitis within the first 2 years after the RSV infection per treatment group will be presented together with the 95% (2-sided) Wilson confidence intervals.

Listings will be provided for the parameters of long-term impact of RSV and its treatment with lumicitabine or placebo for each subject. Listings will also be provided for the clinical diagnosis of eczema and allergic rhinitis within the first 2 years after the RSV infection for each subject.

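### The Screening report opens the SAP's monthly series, but its recall window and lack of a wheezing card make it not comparable with later months

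*SAP*

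**What the plan says.** **Place in the series.** SAP 2.5 fixes the order of the monthly reports: "the entry of the first report is the Screening visit, and each subsequent entry is considered as the next Monthly report". The second report is labelled Month 2. Wheezing outcomes in SAP Table 2 follow the visit variable in the database. For the exploratory burden items, SAP 5.3.2 states: "The results will be presented graphically over time". One Table 3 item, caregiver not employed because of the child's health, names the point outright: it "will be calculated for Screening and each Month as based on the assignment in the database".

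**How the entry report is collected.** Protocol 9.1.2 hands out the cards at the entry visit: "Parents/caregivers will be provided with the medication and wheezing parent/caregiver cards, both of which need to be completed on a daily basis". If entry coincides with the parent study's Day 28 visit, the questionnaire looks back to Day 14. If entry is later, it looks back to Day 28, with a limit: "Any recalled events in the questionnaire will be in the last 30 days or less". Entry may be as late as 3 months after randomization.

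**How later reports are collected.** They cover the time since the last visit or call, one calendar month ±7 days, and the card supports the wheezing answers (Protocol 9.1.3, Time and Events Schedule).

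**Question 7 (work days missed by other family members).** SAP Table 3: "Calculated as the number of days as recorded in question 7 divided by the number of days since the last study visit/telephone call".

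**Medical encounters.** Time and Events Schedule, footnote j: "Medical resource utilization will be monitored throughout the study from signing of the informed consent form until the last study-related activity".

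The SAP has no footnote, exclusion or separate display for the Screening report.

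**The concern.** Wheezing frequency over time is a secondary objective, and the plan meets it with by-month descriptive displays. If the first point is gathered over a shorter period and without the card, a step from Screening to Month 2 mixes the course of disease with a change of method. Episode counts are most exposed, because they are raw numbers per report. A reader who sees episodes roughly double between the first two points could take this for a real rise after RSV infection.

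Question 7 raises a separate problem. For late entry, the days counted and the days divided by may come from different periods.

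**Working it through.** The plan gives no figure of its own to reproduce here. The check is arithmetic on window lengths.

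**Inputs**
- Window W for entry on day e: 14 days if e = 28; otherwise the smaller of 30 and e − 28 (Protocol 9.1.2).
- Later reports: 365.25/12 = 30.44 days, ±7, so 23.44 to 37.44 days (Time and Events Schedule).
- Latest entry: 3 months, taken as Day 91 (3 × 30.44 = 91.3).
- Assumptions: the true rate does not change between the first two reports. Entry days are illustrative.

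**Step 1. Expected episode count at Screening relative to one month = W/30.44**

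| Entry day | W (days) | Ratio to a 30.44-day report | Range, 37.44- to 23.44-day report |
|---|---|---|---|
| 28 | 14 | 0.46 | 0.37 to 0.60 |
| 35 | 7 | 0.23 | 0.19 to 0.30 |
| 42 | 14 | 0.46 | 0.37 to 0.60 |
| 58 | 30 | 0.99 | 0.80 to 1.28 |
| 91 | 30 (capped) | 0.99 | 0.80 to 1.28 |

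The documents give no episode rate. At an assumed constant 1 per month, a 14-day window gives 0.46 expected episodes at Screening and 1.00 at Month 2, a rise of 0.54 from window length alone. At 0.25 and 2 per month the rise is 0.14 and 1.08.

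**Step 2. Percentage of wheezing days per month.** Table 2 defines the numerator and gives no denominator. With a true 10% and a 14-day window, dividing by a full month shows 10 × 14/30.44 = 4.6%. Dividing by the 14 days shows 10%. The text does not settle which applies.

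**Step 3. Question 7 for late entry, if the 30-day cap was applied.** Take 10 days missed within the recalled 30, as an illustration. Over the days recalled: 10/30 = 33%. By the Table 3 formula:
- Entry Day 58: 10/(58 − 28) = 10/30 = 33%, no error.
- Entry Day 75: 10/(75 − 28) = 10/47 = 21%.
- Entry Day 91: 10/(91 − 28) = 10/63 = 16%, which is 30/63 = 0.48 of the value over the days recalled.

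**Step 4. Which feature touches which output**
- No card: wheezing only; direction unknown.
- Window length: raw episode counts, and possibly the percentage of wheezing days. The 0 to 10 burden scores also refer to a different period, but do not scale in proportion to days. The caregiver's own missed-work percentage is already divided by the length of the reported period.
- Encounter capture from consent: encounter counts only, and only if a Screening column is produced.

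**The case against.** Several stronger readings are tempting, and the documents do not support them.

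- **The burden graphs show a switch from recall to diary.** They do not. The wheezing card does not record the burden items, which are recalled at every report. Only their window differs.
- **Table 3 puts a distorted Screening value in the series by name.** The only item that names Screening asks about current employment status, which has no recall window. The place of Screening in the wheezing tables follows from SAP 2.5 together with the visit variable in Table 2.
- **The encounter tables jump from no capture to full capture.** SAP Table 4 and section 7.2 speak of each visit and of months, and do not name Screening. The point is conditional.
- **The question 7 formula is wrong.** As printed in Attachment 2, question 7 asks about the whole time since the last contact and carries no 30-day limit. If caregivers answered it that way, the SAP denominator is right, and dividing by 30 would turn 16% into 33%. The mismatch exists only if the cap in Protocol 9.1.2 was applied.
- **The comparison of arms is biased.** Collection is the same in both groups, and families and investigators are blinded. Unequal entry timing among 7 children is possible but is conjecture.

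It can also be said that no change-from-Screening statistic or test is planned, that listings keep the raw data visible, and that labelling the second report Month 2 after the RSV event suggests entry near Day 28. These points limit the consequence. The last also makes the late-entry question 7 case less likely, but it makes the 14-day window more likely, and there the effect on episode counts is large.

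**Conclusion.** The Screening report is not comparable with later months, and the SAP neither separates nor marks it. At a constant rate, monthly episode counts at Screening would be about 0.46 of a month's for a 14-day window and 0.23 for entry on Day 35, so an apparent rise to Month 2 can come from window length alone. From Day 58 onward the length effect disappears, and only the missing card remains for wheezing. The question 7 percentage is too low for entry after Day 58 if the 30-day cap was used, down to 16% instead of 33% in the Day 91 illustration.

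The damage is mainly to the descriptive time course. The documents do not show an effect on the treatment comparison. The actual size cannot be found, because they give neither entry dates nor wheezing rates.

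**What to change.** - **SAP 5.2.2:** start the by-month wheezing tables with the first report after entry. Show the Screening report separately, labelled as recall without card, with each child's actual window in days. A fixed label of 14 to 30 days would be wrong, because entry on Days 29 to 41 gives fewer than 14.
- **SAP 5.3.2:** mark the Screening point on the burden graphs as having a different recall window. No remark about the card is needed there.
- **SAP Table 3, question 7:** first reconcile the 30-day limit in Protocol 9.1.2 with the wording of question 7 in Attachment 2. Then divide the Screening answer by the days actually recalled. Under the cap this is the smaller of 30 and the days since the last RSV2004 visit, with Day 14 as that visit when entry is on Day 28.
- **SAP 7.2:** if the encounter tables would contain a Screening column, omit it, because encounters are captured only from consent.

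The cost is SAP wording and a table-shell change. The small downside is that the earliest point leaves the wheezing trend tables, though it is still reported.

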**TIME AND EVENTS SCHEDULE**

Study Period	Entry Visit a,b	Assessment Period b				
	Months	0	3 (±7 days)	6 (±7 days)	12 (±7 days)	18 (±7 days)
Screening/Administrative						
Informed consent	X					
Eligibility criteria	X					
Baseline demographics c	X					
Medical and family history c,d	X					
Wheezing and medication parent/caregiver card distribution and verification e,f	X	X	X	X	X	X
Clinical Evaluations						
Clinician questionnaire g	X	X	X	X	X	X
	Monthly telephone calls between study site visits h					
Collection of data from lung function tests and allergy tests (immunoglobulin E and skin tests) i			X			
Medical resource utilization j			X			
Medication l			X			
Safety Evaluations						
Serious/reportable adverse events k			X			

- a. The entry visit needs to take place within 3 months after randomization in Study 64041575RSV2004. The last visit of Study 64041575RSV2004 (ie, Day 28) may be used as the entry visit for this study.
- b. Assessments will be performed during study site visits (entry visit and 3, 6, 12, 18, and 24 months after entry visit in Study64041575RSV2002) and during monthly telephone calls with the parent/caregiver between study site visits.
- c. Baseline demographics and medical/family history from the previous Phase 2 Study 64041575RSV2004 will be captured in the long-term follow-up electronic case report form (eCRF).
- d. Medical and family history to identify risk factors for wheezing/asthma at baseline, including prenatal smoking by the subject's mother, subject's exposure to tobacco smoke, wheezing associated with symptoms of acute respiratory infections, whether the subject has siblings or attends kindergarten/day care, and personal and/or family history of atopy/allergy will be recorded in the eCRF.
- e. Parents/caregivers will be provided with a wheezing parent/caregiver card to be completed daily. The information recorded on the wheezing parent/caregiver card will aid the site responsible person to complete the clinical questionnaire when interviewing the subject's parent/caregiver. Parents/caregivers will be required to return the completed parent/caregiver cards to the study sites every 3 months (eg, in person or by mail/email/fax when no study site visit is scheduled).

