### **9.1.3. Study Period**

No study drug will be administered.

The medical follow-up of the subjects will be performed according to the local standard of care during the assessment period.

At each study site visit (3, 6, 12, 18, and 24 months after entry visit) as noted in the [Time and Events Schedule](#) and during a monthly telephone call (calendar month  $\pm 7$  days), a clinical questionnaire (see [Attachment 2](#)) will be completed by a study site responsible person, by interviewing the subject’s parent/caregiver, to collect the following information:

- Wheezing.  
The parent/caregiver will be provided with a wheezing parent/caregiver card to be completed daily (see [Attachment 3](#)) which will aid the site responsible person in completing the questionnaire.
- Diagnosis of asthma, eczema, and allergic rhinitis. All medical information needed to confirm the diagnosis of asthma, eczema, and allergic rhinitis needs to be collected by the study site personnel.
- Impact of the subject’s health status on normal daily activities for subjects, parents/caregivers, and other family members.

Medical resource utilization data will be collected throughout the study.

Parents/caregivers will also be provided with a medication parent/caregiver card to record medication use on a daily basis (see [Attachment 4](#)).

Parents/caregivers will be required to return the completed wheezing and medication parent/caregiver cards to the study sites every 3 months (eg, in person or by mail/email/fax when no study site visit is scheduled).

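### SAP 2.5 numbers monthly reports by order of entry but treats the number as time since RSV; for late entrants the labels run up to about 2 months early

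*SAP*

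**What the plan says.** SAP 2.5 takes a monthly report's label from its place in the sequence of entries. The first entry is Screening, and "each subsequent entry is considered as the next Monthly report (starting with Month 2, reflecting the time since the RSV event". Study day, in the same section, has another origin: "The reference day is the date of informed consent in study 64041575RSV2002".

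SAP 2.1 gives a different rule for placing assessments: "For assigning assessments, the visit schedule as reported in the database will be used". It adds: "If a subject has a missing visit, the data will be set to missing and will not be imputed". SAP Table 2 (wheezing per month) and SAP 5.3.1 (exploratory items) also take the month from the database. The SAP does not say how these rules fit with 2.5.

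On entry, SAP 1.2 states "Subjects will be enrolled within 3 months after randomization in Study 64041575RSV2004", and footnote a of the protocol's Time and Events Schedule states "The entry visit needs to take place within 3 months after randomization in Study 64041575RSV2004". The same footnote lets the parent study's Day 28 visit serve as entry. Footnote h runs the calls monthly from entry, with a window of 7 days either way. Protocol 9.1.3 counts site visits from entry ("At each study site visit (3, 6, 12, 18, and 24 months after entry visit"), whereas SAP 1.2 places them "at 3, 6, 12, 18, and 24 months after randomization in Study 64041575RSV2004".

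Two kinds of output depend on the label. Protocol 2.1.2 defines the first secondary endpoint by month after the RSV infection. SAP Table 3 defines eczema and allergic rhinitis over the first 2 years after that infection, and counts diagnoses up to the analysis visit labelled Month 24.

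**The concern.** An ordinal number measures elapsed time only if everyone starts at the same point and no step is skipped. Here the starting point may vary by about 2 months, and SAP 2.5 makes no adjustment for entry date. It still says that the label carries time since RSV.

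A by-month table or graph would then put children at different times since infection in the same column. This touches the monthly wheezing percentage and episode counts (SAP Table 2), the Section E summaries and graphs over time (SAP 5.3), medical encounters per month (SAP 7.2), and the Month 24 cut for eczema and allergic rhinitis. The subject count per analysis visit (SAP 4.2) uses the same labels. In groups drawn from 7 children, one child placed in the wrong month can visibly move a monthly mean.

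**Working it through.** Inputs:

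- One month = 365.25/12 = 30.44 days.
- Entry time *e*, in months after randomization: Day 28 is the earliest (28/30.44 = 0.92) and 3 months the latest (Time and Events Schedule, footnote a). Entry at 2 months is taken as an intermediate case.
- Contacts are one month apart, counted from entry (footnote h).
- *m* = number of contacts missed before the report in question.
- Randomization stands in for the RSV event. The highest category in SAP 4.1 puts symptom onset at most 5 days earlier.

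Under SAP 2.5 the report labelled Month L is the L-th entry, with Screening as the first. It falls at *e* + (L − 1) + *m* months, so the label is early by *e* − 1 + *m* months.

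The plan's own label comes first. For Day 28 entry with nothing missed, Month 2 falls at 0.92 + 1 = 1.92 months, so the label is right for the earliest entry. With *m* = 0 throughout:

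| Entry | *e* | Month 2 at *e* + 1 | Month 12 at *e* + 11 | Month 24 at *e* + 23 | Label early by *e* − 1 |
|---|---|---|---|---|---|
| Day 28 | 0.92 | 1.92 | 11.92 | 23.92 | −0.08 |
| 2 months | 2 | 3 | 13 | 25 | 1 |
| 3 months | 3 | 4 | 14 | 26 | 2 |

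The gap between earliest and latest entrants under one label is 4.00 − 1.92 = 2.08 months. Counting from symptom onset adds up to 5/30.44 = 0.16, giving 2.16 months for entry at 3 months. A call made 7 days late adds 7/30.44 = 0.23, giving 2.39.

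**Missed contacts.** If 2.5 is applied literally, the next report received takes the next number. With *m* = 1, labels are early by 0.92, 2 and 3 months for the three entry times. If the database keeps an empty slot for the missed call, as SAP 2.1 permits, this part is zero.

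**Month 24 cut, visits counted from entry (protocol).** With nothing missed, the Month 24 label falls at 23.92, 25 or 26 months. Late entrants can have diagnoses counted up to about 26 months, although the definition says 2 years.

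**Month 24 cut, visits counted from randomization (SAP 1.2).** The final visit is at 24 months and is labelled 24 − *e* + 1, that is 24, 23 or 22. All are inside the cut, so nothing beyond 2 years enters and nothing is lost.

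**The case against.** The strongest reply is that month of follow-up is a legitimate axis. Protocol 2.1.2 introduces the secondary endpoints as covering the follow-up period, Protocol 11.3.2 indexes months within follow-up years, and calls run from entry. On that view only the remark about time since RSV is wrong, and a footnote would cure it. A follow-up axis could indeed have been chosen, but the SAP did not choose it. Calling the first report after entry Month 2 makes sense only on a time-since-RSV scale with entry near Day 28, and the endpoint and the two-year cut are both worded from the infection.

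The second reply concerns missed contacts, and it stands. A reader might infer from 2.5 that every missed contact shifts later labels. The documents do not establish this, because SAP 2.1, Table 2 and 5.3.1 refer to the database schedule, which may hold the empty place. What remains is that the SAP does not reconcile the rules.

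Third, a reader might infer that a child with no Month 24 label loses eczema or allergic rhinitis diagnoses. That is not so: the cut is an upper limit, and a missing label excludes nothing.

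Fourth, SAP 5.2.1 already places episodes by start date, and listings show the reported data. This helps only in part, because the intervals to which episodes are allocated are themselves the labelled visits.

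Finally, there are 7 children and no testing. That limits the consequence but does not make the label correct. Counting study day from consent is not itself a fault, since the SAP does not present study day as time since RSV.

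**Conclusion.** The late-entry part holds. For permitted entry times and no missed contact, the SAP 2.5 label is accurate at Day 28 entry and up to about 2 months early at 3-month entry, and one label can pool children about 2 months apart. The further month per missed contact is conditional on applying 2.5 literally. The Month 24 cut can over-include, to about 26 months, for late entry when visits are counted from entry.

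A reader might infer that the primary results are distorted. They are not: SAP 5.1.1 derives asthma from all questionnaires up to the final visit, and divides wheezing days by the time from consent to study completion. Neither uses the month label. Nor do the documents show that any of the 7 children is mislabelled, because they give no actual entry dates or missed contacts. The sizes above are the range the plan permits, with randomization as the origin. The effect is on interpretation of descriptive output, not on any error rate. The rule should still be changed, because it gives a wrong result for permitted entry times and is cheap to correct.

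**What to change.** In SAP 2.5, derive the month from the contact date relative to randomization in Study 64041575RSV2004, and state that this one rule also governs SAP 2.1, Table 2 and 5.3.1. Then:

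- Leave a month empty when no contact covers it.
- Assign wheezing days, episode starts and medical encounters to months by their own recorded dates where these are complete.
- Keep Section E items, which ask about the time since the last contact, with the month of that contact, and flag reports spanning more than one month.
- Cut eczema and allergic rhinitis at 2 years after randomization by the diagnosis date recorded in Sections C and D of the questionnaire (Protocol Attachment 2).

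The cost is SAP wording and light reprogramming for 7 children. A merge rule is needed when two reports fall in one month; SAP 2.1 already merges unscheduled visits. Late entrants will have empty or partly observed early months. For entry at 3 months the entry questionnaire reaches back only 30 days (Protocol 9.1.2), to 3 − 30/30.44 = 2.01 months, so about the first 2 months are empty. Section E totals that span two months can be flagged but not split.
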